7.2 Primary Effectiveness Endpoint

The primary effectiveness endpoint is the rate of effective closure of the PDA among subjects with a successful device implant as assessed by the presence of either a Grade 0 or Grade 1 shunt (see **Appendix A** for definition) at the 6 month follow-up visit by transthoracic echocardiography.

The proportions of subjects who have effective closure of the PDA at follow-up will be calculated along with the 95% confidence interval. The numerator for the event rate is the number of subjects who have effective closure of the PDA at follow-up. The denominator is the number of subjects in the analysis population (As detailed in Section 7.4). The primary effectiveness endpoint will be compared with the rate reported in the ADO II AS and Continued Access Protocol studies.

Among subjects successfully implanted with any device, the PDA occlusion rate is estimated to be approximately 99%.

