Effectiveness Endpoint: The effectiveness endpoint is the rate of effective closure of the PDA using a transcatheter device within six months post procedure. If more than one attempt is required, or multiple devices are required during the same procedure, it is still considered effective if there is Grade 0 or Grade 1 shunt, as defined below, at follow-up (within six months) by transthoracic echocardiography (TTE) or if a second procedure is not required following the initial attempt. If there is device embolization, adjacent vessel stenosis that required retrieval of the device and replacement during the same procedure with less than Grade 1 shunt during follow-up, it is still considered effective. Conversely, if an AE is noted after the procedure that requires a second procedure for treatment that results in greater than Grade 1 shunt, then the procedure is considered not effective, even if the initial attempt was effective.

PDA shunt definition:

Grade 0—none;

Grade 1—trivial (narrow jet adjacent to the device via the PDA). Note: the presence of flow via existing or newly formed aortopulmonary collaterals should not be considered as representing a shunt via the PDA. (See references in **Appendix B** by Skinner and Acherman)

Grade 2—mild (broader jet filling proximal left pulmonary artery branch and extending to main pulmonaryartery);

Grade 3/4—moderate to severe (wide jet filling the main pulmonary artery and extending to pulmonary valve or distal pulmonary artery branches, which also may be accompanied with the presence of flow reversal in the abdominal aortic Doppler pattern during diastole)

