7.4 Analysis Population

The analysis of the primary and secondary endpoints will include all subjects who achieve a successful implant, which is defined as leaving the catheterization lab with a device implanted in the PDA. If a subject has multiple devices attempted during the same procedure, but leaves procedure with at least one device within the PDA the procedure is considered successful. Subjects without an implanted device in the PDA will be excluded. Additionally, subjects who had no follow- up visits up to the six-months +/- one-month window, or lost to follow-up will be excluded.

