7.6. Justification of Clinical Study Design

Based on the IMPACT registry, there are over 6000 transcatheter device closures of PDA that occurs in the United States annually. However, there are no comprehensive data collection tools for this procedure. The current databases do not include multiple data points, or follow-up data, or a section for specific adverse events to be documented. Moreover, until now, there has been no approved devices for PDA closure in children < 2kg. This clinical study is the first of its kind to collect data from all transcatheter device closure of PDA in children < 2kg performed at the CCISC participating centers. This study will be limited to children between 700 to 2000 grams who are the most vulnerable population undergoing this procedure. This will allow us to understand the real world experience (efficacy and safety) of using the Amplatzer Piccolo Occluder device in an extremely vulnerable, yet highly underserved population. The study will allow for standardization of this procedure throughout the country for the small children (<2 kg) with a PDA. This is a multicenter, single arm, observational data collection study. This will be a large population study to help analyze outcomes in subjects <2 kg. The trial has two primary endpoints for safety and effectiveness without formal hypothesis. The safety and effectiveness results will be compared with data reported in the Amplatzer Piccolo Occluder IDE and Continued Access Protocolstudies.

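### Sections 2.1 and 7.2 define the primary effectiveness rate incompatibly, so infants who die or miss the 6-month echo after an earlier visit count against closure under one and can be successes under the other

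*Protocol*

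**What the plan says.** **Numerator, Section 7.2.** The opening sentence defines effective closure, among successfully implanted infants, as a Grade 0 or Grade 1 shunt "at the 6 month follow-up visit by transthoracic echocardiography". The counting sentence is looser and names no month: "The numerator for the event rate is the number of subjects who have effective closure of the PDA at follow-up".

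**Numerator, Section 2.1.** The same primary endpoint is introduced as closure within six months of the procedure. Where more than one attempt or device was needed, "it is still considered effective if there is Grade 0 or Grade 1 shunt, as defined below, at follow-up (within six months") by TTE, "or if a second procedure is not required following the initial attempt". A later adverse event whose treatment needs a second procedure and leaves more than a Grade 1 shunt turns the case into a failure.

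**Denominator, Section 7.4.** "The analysis of the primary and secondary endpoints will include all subjects who achieve a successful implant". Infants with no device in the duct are removed. In addition, "subjects who had no follow- up visits up to the six-months +/- one-month window, or lost to follow-up will be excluded". Death is not mentioned.

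**Visits and attrition.** Appendix E schedules TTE within 48 hours, at 30 ± 7 days and at 6 ± 1 months. Under Section 6, missing the 6-month visit is a missed visit and a deviation. Loss to follow-up requires two missed visits plus at least two failed telephone calls. Death is tabulated on its own in Section 7.5e.

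**The concern.** An infant with Grade 0 at 48 hours and at 30 days who dies at three months of a complication of prematurity has had follow-up visits and is not lost to follow-up. On the plain reading of 7.4 this infant stays in the denominator. Under 7.2 there is no 6-month TTE, so the infant cannot be counted as closed. The same holds for an infant who misses only the 6-month visit, or who attends without a shunt grade being recorded. Under 2.1, each of them can be a success.

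Such cases are foreseeable. Section 7.6 describes these infants as those "who are the most vulnerable population undergoing this procedure". Section 3.1 requires no follow-up testing beyond usual practice, and Section 8.1 accepts that incomplete echo detail may not be a deviation.

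The resulting rate is to be set beside the earlier device studies and beside an expected 99%. If deaths and absent echoes lower it, the shortfall would look like weaker device performance. Whether it appears at all depends on which section the analyst follows.

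**Working it through.** **Inputs**
- Expected closure 99% (Section 7.2). This is the protocol's estimate and is not derived from anything that could be reproduced.
- 500 infants (Section 2), a limit on data collection with no sample-size calculation behind it. It is used here as the size of the analysis population, for illustration.
- m, the share of the 7.4 population with an earlier visit but no 6-month shunt grade. The protocol gives no figure, so m is assumed and shown over a range.

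**Where each infant falls**

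| Implanted infant | 7.4 denominator (literal) | Success under 7.2 | Success under 2.1 |
|---|---|---|---|
| Grade 0/1 at 6 months | in | yes | yes |
| Grade 0/1 earlier, then dies | in | not possible | possible |
| Grade 0/1 earlier, misses only 6 months | in | not possible | possible |
| Meets lost-to-follow-up definition | out | – | – |
| No follow-up visit at all | out | – | – |

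**Formula.** Under 7.2 with 7.4, rate = 0.99 × (1 − m):
- m = 2%: 0.99 × 0.98 = 97.0%
- m = 5%: 0.99 × 0.95 = 94.1%
- m = 10%: 0.99 × 0.90 = 89.1%
- m = 15%: 0.99 × 0.85 = 84.2%

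**In whole infants** (500 analysed; closed = 99% of those with a 6-month grade, rounded; exact binomial 95% intervals). The last column counts every infant without a 6-month grade as a success, as 2.1 would allow if each was last seen closed or needed no second procedure.

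| m | No 6-month grade | Closed at 6 months | 7.2/7.4 rate (95% CI) | Only those with a 6-month grade | 2.1 reading |
|---|---|---|---|---|---|
| 0% | 0 | 495 | 99.0% (97.7–99.7) | 99.0% | 99.0% |
| 2% | 10 | 485 | 97.0% (95.1–98.3) | 485/490 = 99.0% | 495/500 = 99.0% |
| 5% | 25 | 470 | 94.0% (91.5–95.9) | 470/475 = 98.9% | 495/500 = 99.0% |
| 10% | 50 | 446 | 89.2% (86.1–91.8) | 446/450 = 99.1% | 496/500 = 99.2% |
| 15% | 75 | 421 | 84.2% (80.7–87.3) | 421/425 = 99.1% | 496/500 = 99.2% |

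Each 1% of infants without a 6-month grade costs the 7.2/7.4 rate about one percentage point. With six such infants (1.2%) the result is 489/500 = 97.8%, with an upper limit of 98.9%, just below the expected 99%.

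**The case against.** A reader might infer that the protocol has a rule scoring death and missed visits as failed closure. The documents do not support that. No sentence says so. It follows only from joining the first sentence of 7.2 to the literal 7.4 population, and 2.1 contradicts it. The counting sentence in 7.2 does not itself name six months. Infants lost to follow-up, or never seen after the procedure, are already excluded, so only some missed visits are affected.

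The 7.4 exclusion could also be read as no visit inside the 6-month window, which would remove these infants. That reading is less natural, because the wording runs up to the window and so covers the whole period. If it is intended, 7.4 should say so.

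The success wording in 2.1 is also attached to cases with several attempts or devices, so extending it to a single-device closure is an inference. The opening sentence of 2.1, closure within six months, nevertheless covers everyone.

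Handling of missing data is commonly left to a SAP, which is not shown. That is fair for sensitivity analyses. It does not cover a numerator and denominator that the protocol itself fixes, and fixes in two ways.

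Finally, Section 7.6 states that there is no formal hypothesis, so an interval lying below 99% fails no test. Deaths and losses to follow-up are tabulated in 7.5, which would help a reader interpret a shortfall, although missing 6-month echoes are not listed there. These points limit the severity and leave the conflict in place.

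**Conclusion.** The concern stands as an inconsistency between 2.1 and 7.2 on time point and success criterion, with a consequence that depends on which is followed. Under 7.2 with 7.4 read literally, infants with an earlier visit who die or lack only the 6-month grade lower the closure rate. Under 2.1 they need not. At m = 10% the gap is about 89% against about 99%, and at m = 2% it is 97.0% against about 99%.

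These sizes rest on 99% true closure, on closure being unrelated to whether a 6-month grade exists, and on values of m that the protocol does not supply. The direction under 7.2/7.4 does not depend on the chosen m. The result at stake is an estimate and its descriptive comparison with earlier studies, so this should be corrected before analysis, but no decision rule is broken.

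**What to change.** Reconcile Sections 2.1, 7.2 and 7.4 to one time point and one success criterion. Editing 7.2 alone would leave two definitions of the primary endpoint.

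If a 6-month rate is wanted:
- Make the denominator the implanted infants whose 6-month closure status is determined: those with a 6-month TTE grade, plus those with a failure already established, such as a second procedure leaving more than a Grade 1 shunt.
- Report deaths before six months and missing 6-month TTEs as separate counts.
- Show two bounds: the last observed grade carried forward to six months, and all undetermined infants counted as failures.

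This denominator is slightly asymmetric. It keeps early failures and drops infants last seen closed, which pulls the rate down a little. For illustration, suppose that of 50 infants without a 6-month grade, one had an established failure and 49 were last seen closed. The determined rate is 446/451 = 98.9%, and carrying the last grade forward gives (446 + 49)/500 = 99.0%. The first bound therefore shows the size of the asymmetry.

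The cost is a short edit to three sections and a few tabulations from data already scheduled for collection. The downside is a smaller denominator and an assumption that undetermined infants resemble the rest, which the two bounds display.

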7.3 Secondary Endpoints

The secondary endpoint is the rate of significant obstruction of the pulmonary artery or aorta through the follow-up visit per the following definitions:

1. Significant obstruction of the left pulmonary artery is defined as less than 30% flow to the left lung by lung perfusion scan or a peak instantaneous gradient in left pulmonary artery ≥35 mmHg by echocardiogram if lung perfusion scan is not available. OR

2. Significant obstruction of the aorta is defined as a gradient of ≥ 20 mmHg in the aortic isthmus by invasive aortic catheterization or a mean gradient ≥ 20 mmHg in the aortic isthmus by echocardiogram if invasive aortic catheterization is not available.

The proportions of subjects experiencing an obstruction of the pulmonary artery or aorta through the of low-up visit will be calculated along with the 95% confidence interval. The numerator for the event rate is the number of subjects who experience an event by the follow-up visit. The denominator is the number of subjects in the analysis population (As detailed in Section 7.4).

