4.4 Post-Procedure Follow-up

The follow-up assessment must be obtained within 48-hoours, 1-month and 6-months after the procedure. The schedule of all assessments is provided in Appendix E. The following post-procedure follow-up assessments, diagnostic tests and evaluations and must be included in the PDA module:

- a. Demographics- including subject's age, weight
- b. Transthoracic echo (TTE) including checking for the presence of the device within the PDA, degree of residual shunting if any, spectral Doppler findings, estimates of pulmonary

hypertension, left ventricular function and dimensions, pulmonary and aortic flow and dimensions, pulmonic and tricuspid valve regurgitation

Subjects should be on appropriate endocarditis prophylaxis according to the American Heart Association recommendations for prophylaxis.

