8 REQUIREMENTS FOR INVESTIGATOR RECORDS AND REPORTS

8.1 Deviations from Clinical Study Protocol (CSP)

A deviation is defined as an instance(s) of failure to follow, intentionally or unintentionally, the requirements of the CSP. The investigator should not deviate from the CSP. In some cases, failure to comply with the CSP may be considered failure to protect the rights, safety and well-being of subjects; such non-compliance exposes subjects to unreasonable risks. Examples: failure to adhere to the inclusion/exclusion criteria, failure to safeguard protected health information (PHI) failure to perform safety assessments intended to detect adverse events. Investigators should seek to minimize such risks by adhering to the CSP.

If certain assessments such as details of the echocardiogram, RSS, etc., is not performed or completed within the CRF, it may not be considered as a deviation as determined by the National PI. The PI must maintain accurate, complete, and current records, including documents showing the date of and reason for each deviation from the CSP. Relevant information for each deviation will be documented as soon as possible on the applicable CRF within the PDA module. The site will submit the CRF to the CCISC PDA Module PI. The PI is required to adhere to local regulatory requirements for reporting deviations to IRB. An investigator shall notify the CCISC PDA Module PI and the reviewing IRB of any deviation from the investigational plan to protect the life or physical well- being of a subject in an emergency. Such notice shall be given as soon as possible, but in no event later than10 working days after the emergency occurred. The protocol deviation reporting form and a log are provided in Appendix F.

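### Section 7.3 keeps infants with no usable vessel assessment in the denominator, so the reported obstruction rate is only a lower bound

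*Protocol*

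**What the plan says.** **Numerator and denominator.** Section 7.3 fixes both. On the numerator: "The numerator for the event rate is the number of subjects who experience an event by the follow-up visit". On the denominator: "The denominator is the number of subjects in the analysis population (As detailed in Section 7.4".

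**Population.** Section 7.4 begins: "The analysis of the primary and secondary endpoints will include all subjects who achieve a successful implant". After removing infants who leave without a device in the duct, it adds one restriction: "Additionally, subjects who had no follow- up visits up to the six-months +/- one-month window, or lost to follow-up will be excluded". Neither sentence asks whether the vessels were assessed.

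**Event definition.** Section 7.3 defines both components by a measured value. For the left pulmonary artery it is "less than 30% flow to the left lung by lung perfusion scan or a peak instantaneous gradient in left pulmonary artery" at or above a threshold. For the aorta it is a catheter gradient or, failing that, a mean gradient "in the aortic isthmus by echocardiogram if invasive aortic catheterization is not available".

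**Six-month summary.** Section 7.5c reports the frequency and percentage of each obstruction at the 6-month visit among subjects with a successful implant. It does not repeat the follow-up exclusion.

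**The concern.** An infant who stays in the denominator but has no usable assessment cannot enter the numerator. The protocol never says that such infants are event-free, but its division treats them so. The same applies in part to an infant assessed only early: Section 2.1 recognises that vessel stenosis can appear late, yet one early visit can be enough to stay in a rate that runs through six months.

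This is the only secondary endpoint, and it concerns harm from the device to adjacent vessels. Missing assessments can only make the device look safer on it. A reader of the final table could not tell how many infants were actually examined.

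**Working it through.** **1. Can unassessed infants occur?** The relevant sections side by side:

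- Section 4.4 says "The follow-up assessment must be obtained within 48-hoours, 1-month and 6-months after the procedure", and Appendix E schedules a transthoracic echo at all three visits. The Section 4.4 list names spectral Doppler findings and pulmonary and aortic flow, but not a gradient as such.
- Sections 3.1 and 4 say that the study requires no special follow-up testing.
- Section 8.1 says that if "details of the echocardiogram, RSS, etc., is not performed or completed within the CRF, it may not be considered as a deviation", with the classification left to the National PI.
- Section 6 calls a subject lost only after two missed visits and at least two failed phone calls. An infant seen only at 48 hours whose family can still be reached is neither lost nor, read literally, without a follow-up visit. If Section 7.4 means no visit inside the 6-month window, fewer such infants remain, but an assessment is still not required.
- Section 6.3 provides no core laboratory that would read missing values from the images.

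Such infants are therefore possible under the rules. Their number cannot be derived.

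**2. Direction.** Let N be the analysis population, x_A the obstructions among assessed infants and x_U those among unassessed infants.

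- Actual proportion: (x_A + x_U)/N
- Reported proportion: x_A/N
- Shortfall: x_U/N, which is zero or positive

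The reported rate can be too low or correct on this account, never too high.

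**3. Size, under assumptions.** There is no figure in the protocol to reproduce. Assumed inputs are the true rate p, the unassessed share m, and assessment unrelated to obstruction. The reported rate is then p × (1 − m):

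| p | m = 10% | m = 20% | m = 40% |
|---|---|---|---|
| 2% | 1.8% | 1.6% | 1.2% |
| 5% | 4.5% | 4.0% | 3.0% |

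**4. Precision.** N = 500 (Sections 2 and 13) is the planned cohort and so an upper limit for the analysis population. Section 7.3 names no interval method, so the exact binomial of Section 7.1 is used. With p = 2% and m = 40%, 300 infants are assessed and 6 events are seen:

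- Protocol rule: 6/500 = 1.2% (0.44 to 2.59), width 2.15 points
- Assessed only: 6/300 = 2.0% (0.74 to 4.30), width 3.56 points, a ratio of 3.56/2.15 = 1.66

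With no events, the upper limit is 0.74% for n = 500 and 1.05% for n = 350.

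**5. The opposite error.** Suppose every obstructed infant is assessed and a share m of unobstructed infants is not. The protocol rule is then exact, and the assessed-only rate is p/[p + (1 − p)(1 − m)]. For p = 2%:

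- m = 10%: 0.02/0.902 = 2.22%
- m = 30%: 0.02/0.706 = 2.83%

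**6. Bounds.** Counting the unassessed first as free and then as obstructed, for p = 2% among those assessed:

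- m = 10%: 9/500 = 1.8% to (9 + 50)/500 = 11.8%
- m = 40%: 6/500 = 1.2% to (6 + 200)/500 = 41.2%

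**The case against.** A reader might infer that the rate is biased downward as a matter of fact. The protocol does not support that. The shortfall is zero if no unassessed infant is obstructed, and parts of the text point to detection on suspicion. Section 5.5.3 sets out a work-up when stenosis is suspected or noted, and vessel stenosis has its own fields on the adverse event form. An infant with an echo and no recorded gradient may have had nothing to measure. Echo with Doppler is scheduled three times, so an infant is wholly unassessed only if all three lack usable data. This stands, and it is why the result is called a lower bound rather than a biased rate.

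A reader might also take Section 8.1 as waiving the echo measurements. It does not: it gives the National PI discretion over whether a gap is a deviation, and the Section 4.4 requirement remains.

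Nor is a gradient, scan or catheterization the only route to a finding. Section 5.5.3 also names CT or MR angiography and, for the aorta, a clinical exam.

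Finally, missing-data rules often sit in a SAP, and Section 7.5c says only who is included. An SAP not seen here could add such rules. But Section 7.3 already fixes numerator and denominator, and an SAP that follows it inherits the result. Section 7.6 states that there is no formal hypothesis, so no test or decision rule is affected. That limits the consequence but does not make the denominator right.

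**Conclusion.** The point holds in this form. Sections 7.3 and 7.4 together produce a lower bound for the obstruction rate and present it as the estimate, with an interval that treats unassessed infants as if they supplied information. Read literally, Section 7.5c does so more strongly, because it also keeps infants with no follow-up at all.

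The size is not known. The illustration of 2% reading 1.8% at 10% unassessed and 1.2% at 40% rests on an assumed true rate, assumed missingness, and assessment unrelated to obstruction. At low missingness the effect is small. At high missingness the point estimate and the interval both mislead, and nothing in Section 7.3 requires the number assessed to be shown.

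**What to change.** **Section 7.3.** Define the evaluable set for the composite as subjects with a qualifying assessment of both vessels in the follow-up window, or with an obstruction found in either vessel. Qualifying assessments are an echo gradient, a perfusion scan, catheterization, or the CT/MR imaging named in Section 5.5.3. State the window, so that it is clear that a 48-hour echo alone does not make an infant evaluable through six months. Sections 5.5.3 and 7.3 should also be reconciled on which findings count, since the endpoint definition in 7.3 mentions neither CT/MR nor a clinical exam.

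**Section 7.5c.** For each vessel, use subjects assessed for that vessel at 6 months.

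**Reporting.** Give the number not assessed and three rates side by side: the current all-subjects rate as the lower bound, the evaluable-set rate, and an upper bound counting unassessed subjects as obstructed.

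**Cost.** A few sentences and table rows, and no added testing. The interval widens: by about two thirds in the 40% example, much less if few are unassessed. The evaluable-set rate may err upward if gradients are recorded mainly on suspicion. Admitting infants with one obstructed vessel, but not those with only one clear vessel assessed, pushes the same way. Both bounds are shown for that reason, although the upper one says little when many are unassessed.
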